6.4.2 Known Potential Benefits

This research involves no prospect of direct benefit to individual subjects but is likely to yield generalizable knowledge about the subject's disorder or condition.

7 COLLABORATIVE AGREEMENTS

7.1 AGREEMENT TYPE

NHLBI is in the process of putting together a Research Collaborative Agreement. Once the agreement is executed, more details will be provided.

Transfers that are associated with correlative studies conducted under an approved protocol: [name] will be receiving coded samples from the University of Maryland Baltimore. He will be conducting measurements of HIV reservoir size (HIV DNA PCR, cell-associated RNA PCR) and soluble factors in plasma such as D-dimer, CRP, IL-2, IL-4, IFNg, TNF-a and other cytokines.

Investigators in the NIH intramural program may participate in multi-site clinical trials (either as a site or as the coordinating center) under which human materials are transferred from the intramural program to another site for correlative studies that are part of the approved protocol. In such a situation, the protocol clearly documents the tests conducted under the correlative studies, and each institution participating in the clinical study is bound by the terms of their Protocol and their obligations under the statutes and regulations. In addition, intramural protocols are cleared by the IC Clinical Director. In such situations, use of an HM-MTA is not necessary for these transfers.

8 CERTIFICATE OF CONFIDENTIALITY

To further protect the privacy of study participants, a Certificate of Confidentiality has been issued by the National Institutes of Health (NIH). This certificate protects identifiable research information from forced disclosure. It allows the investigator and others who have access to research records to refuse to disclose identifying information on research participation in any civil, criminal, administrative, legislative, or other proceedings, whether at the federal, state, or local level. By protecting researchers and institutions from being compelled to disclose information that would identify research participants, Certificates of Confidentiality help achieve the research objectives and promote participation in studies by helping assure confidentiality and privacy of participants.

9 INSURANCE BILLING

The NIH will not bill any insurance companies or participants for any research or related clinical care as the NIH is not a HIPPA-covered entity,

10 COMPENSATION, REIMBURSEMENT, AND PAYMENT

If a participant requires it, transportation to the NIH will be arranged by the UMB study staff. Participants will receive \$200 cash after they have completed each FDG PET/CT from the UMB study staff.

If a participant is unable to finish the optional study after they arrive at the NIH for some reason, they will receive \$100 from the UMB study staff.

All compensation will be given to the participant by a UMB study team member at their next visit to UMB.

This study does not offer reimbursement for or payment of travel, lodging or meals.

APPENDIX A: SAFETY MONITORING BOARD AND PLAN

Full Title:	CD24Fc Administration to Decrease LDL and Inflammation in HIV Patients, Both as Markers of Efficacy and Cardiovascular Risk Reduction	
Short Title:	CALIBER	
Clinical Phase:	II	
IND Sponsor:	Oncolmmune, Inc.	
Principal Investigator:	[name] PhD	
Sample Size:	n = 64	
Accrual Ceiling:	110	
Study Population:	Adults age 50 or older with chronic HIV infection who have achieved viral suppression with use of ART for at least 2 years	
Accrual Period:	18 months	
Study Design:	This is a double blind, placebo controlled, randomized trial to evaluate the safety of CD24Fc in adults with HIV. Patients will be randomized to two arms: (1) CD24Fc (IV) for 3 doses over 6 weeks vs (2) Placebo (IV) for 3 doses over 6 weeks	
Study Duration:	Start Date: January 2020	
	End Date: December 2021	
Study Agent:	CD24Fc 240mg IV Infusion	
Primary Objectives:	 To determine the safety and tolerability of CD24Fc during the 4-week dosing period and a 24-week follow-up period in a cohort of HIV patients. 	
	 To evaluate the change in LDL during a 4-week dosing period of CD24Fc and a 24-week follow-up period. 	
Secondary Objectives:		
	1. Levels of total cholesterol, HDL, and triglycerides	
	 Markers of immune activation (CD4 and CD8 T cells, IFN, TNF, sCD14) 	
	3. Size of HIV reservoirs	
	4. Myocardial damage (measured by Troponin I and T)	
	5. Hepatic steatosis, as determined by transient elastography	
	 6. Leptin 7. Hemoglobin A1c 	
	 Presence of anti-drug antibody (ADA) and temporal correlation to any adverse events, and its effect on PK (For first 6 subjects). 	
	 The pharmacokinetics (PK) and pharmacodynamics (PD) of CD24Fc in the first 6 randomized subjects. 	
	10. Changes in IL-6, apoB, Lp(a), urine albumin to creatinine ratio before and after treatment.	

Exploratory Objectives:	
	 To assess the effect of CD24Fc on aortic vascular inflammation as measured by standardized uptake value of arterial FDG by PET/CT. We will select 12 subjects with an LDL>125 to have the imaging study. To assess the effect of CD24Fc on the inflammatory markers hs- CRP and GlycA. To assess the effect of CD24Fc on the CEC and NMR lipoproteins. To assess the effect of CD24 Fc on endothelin-1.
Primary Endpoints:	 Incidence and severity of any adverse events (AEs) during the administration of drug and 24 weeks after completion. Safety will be evaluated by assessment of clinical laboratory tests, physical examination at various time points during the study, and by the documentation for AEs. The percentage reduction in LDL level from the baseline (predosing) to 2 weeks after the last treatment.
Secondary Endpoints:	
	 Percent change in levels of total cholesterol, HDL, and triglycerides from baseline to Week 6 and 28 between placebo and intervention arms. Percent change in markers of immune activation (CD4 and CD8 T cells, IFN, TNF, sCD14) from baseline to Week 6 and 28 between placebo and intervention arms. Change in proviral DNA from baseline to Week 6 and Week 28 between placebo and intervention arms. Change in proviral DNA from baseline to Week 6 and Week 28 between placebo and intervention arms. Percent change from baseline to week 28 in Troponin I and T between placebo and intervention arms. Change in percent of hepatic steatosis (by CAP measurement) and fibrosis (by KPA) as determined by transient elastography from baseline to week 28 between placebo and intervention arms. Percent change in leptin from baseline to Week 6 and Week 28 between placebo and intervention arms. Percent change in leptin from baseline to Week 6 and Week 28 between placebo and intervention arms. Percent change in hemoglobin A1c from baseline to Week 6 and week 28 between placebo and intervention arms. PK and PD assessments (For 6 subjects; presence of ADA and its
Exploratory Endpoints:	effect on PK in all subjects 1. Change in vascular inflammation as evidenced by aortic FDG uptake by FDG-PET/CT will be assessed before and after therapy. The arterial uptake of FDG is measured by the standardized uptake value (SUV) max divided by the venous SUV mean yielding a target to background ratio (TBR). 2. Changes in hs-CRP and GlycA before and after treatment. 3. Changes in CEC and NMR lipoproteins before and after treatment.

4. Changes in endothelin-1 before and after treatment.

Adverse Events, Serious Adverse Events, and Unanticipated Problems

The investigator will grade the severity of each adverse event (AE) according to the "Division of AIDS Table For Grading The Severity Of Adult And Pediatric Adverse Events", version 2.1, July 2017. https://rsc.niaid.nih.gov/sites/default/files/daidsgradingcorrectedv21.pdf

For AEs not included in the protocol defined grading system, severity will be determined using the guidelines outlined in the protocol. All AEs must have their relationship to study intervention assessed by the clinician who examines and evaluates the participant based on temporal relationship and his/her clinical judgment. The degree of certainty about causality will be graded using the categories outlined in the protocol. The investigator will record nonserious adverse events and report them to the sponsor within 30 days of the event occurrence.

The PI will be responsible for determining whether an AE is expected or unexpected. An AE will be considered unexpected if the nature, severity, or frequency of the event is not consistent with the risk information previously described for the study intervention. All AEs will be followed to adequate resolution. AEs will be collected between Day 0 and Week 28 (completion of study).

The PI or study coordinator will record all reportable events with start dates occurring any time after informed consent is obtained until the last day of study participation. At each study visit, the investigator will inquire about the occurrence of AE/SAEs since the last visit. Events will be followed for outcome information until resolution or stabilization.

Events will be summarized on the basis of the date of onset for the event. A treatment-emergent adverse event will be defined as any new or worsening adverse event that begins on or after the date of first dose of study drug up until study completion. Summaries (number and percentage of subjects) of treatment-emergent adverse events will be provided at study completion.

Serious Adverse Events (SAEs)

SAEs that occur after the study follow-up period that are reported to and are assessed by the Investigator to be possibly, probably, or definitely related must be reported to the Medical Monitor.

The study clinician will immediately report to the sponsor any serious adverse event, whether or not considered study intervention related, including those listed in the protocol or investigator brochure and must include an assessment of whether there is a reasonable possibility that the study intervention caused the event. Study endpoints that are serious adverse events (e.g., all-cause mortality) must be reported in accordance with the protocol unless there is evidence suggesting a causal relationship between the study intervention and the event (e.g., death from anaphylaxis). In that case, the investigator must immediately report the event to the sponsor.

All serious adverse events (SAEs) will be collected between Day 0 and Week 28 and followed until satisfactory resolution or until the site investigator deems the event to be chronic or the participant is stable.

Unanticipated Problems

The investigator will report unanticipated problems (UPs) to the reviewing Institutional Review Board (IRB) and to the lead PI. The UP report will include the following information:

- Protocol identifying information: protocol title and number, PI's name, and the IRB project number;
- A detailed description of the event, incident, experience, or outcome;
- An explanation of the basis for determining that the event, incident, experience, or outcome represents an UP;
- A description of any changes to the protocol or other corrective actions that have been taken or are proposed in response to the UP.

To satisfy the requirement for prompt reporting, UPs will be reported using the following timeline:

- UPs that are serious adverse events (SAEs) will be reported to the IRB and to the study sponsor within 3 days of the investigator becoming aware of the event.
- Any other UP will be reported to the IRB and to the study sponsor within 15 days of the investigator becoming aware of the problem.
- All UPs should be reported to appropriate institutional officials (as required by an institution's written reporting procedures), the supporting agency head (or designee), and the Office for Human Research Protections (OHRP) within 30 days of the IRB's receipt of the report of the problem from the investigator.

Pausing and Halting Rules

Enrollment and dosing will be paused for an individual subject who has a Grade 4 AE. After review by the Medical Monitor (MM) and reporting to the DSMB in the regularly scheduled report every 12 weeks, the MM will evaluate whether study participation for the subject should continue. During MM review, enrollment and dosing will not be paused for other study subjects.

If two subjects experience the same Grade 4 AE related to the study drug, all enrollment will be paused and all doses for enrolled subjects will be held. The MM will report to the DSMB within 24 hours and study dosing will halt until DSMB determination regarding continuation of study enrollment and dosing.

If one or more subjects experiences changes in mental status, DIC, dyspnea, cytokine release syndrome and/or hypotension related to the study drug, without remediation in 2-4 hours, the MM will report to the DSMB within 24 hours and the DSMB will review the report for possible study termination. During this review, enrollment and dosing will be halted for all subjects.

Safety and Efficacy Analyses

The primary safety endpoint will be assessed by Incidence and severity of any adverse events (AEs) during the administration of drug and 24 weeks after completion. Safety will be evaluated by assessment of clinical laboratory tests, physical examination at various time points during the study, and by the documentation for AEs. A statistical analysis plan (SAP) will be prepared and finalized prior to unblinding of subject's treatment assignment. This document will provide further details regarding the definition of analysis variables and analysis methodology to address all study objectives.

Safety and tolerability will be summarized by treatment arm, including Treatment Emergent Adverse events (TEAEs), and laboratory evaluations. No inferential analysis is planned for safety data. Adverse events will be coded using the most current version of the Medical Dictionary for Regulatory Activities

(MedDRA). TEAEs are defined as new or worsening AEs after the first dose of study medication, and will be summarized by system organ class, and preferred term. A list of subjects who have Severe Adverse Events (SAEs) and who discontinue from the study due to an adverse event will be provided.

Summary statistics for laboratory values will be provided at baseline, post baseline, and for changes from baseline to post baseline. Vital signs will also be summarized in the same way. Occurrence of significant laboratory abnormalities will be tabulated. All medications administered during the study period must be documented on the Concomitant Medication electronic case report form (eCRF). These medications will be coded using the most current version of the World Health Organization Drug Dictionary. A listing of all medications including the reported term, dictionary term, start and stop dates, and other relevant data will be provided. The Safety Analysis Set (SAF) will include all subjects who received at least 1 dose of study medication and the subjects will be analyzed as treated. The safety and efficacy analyses will be summarized based on the SAF.

The following analysis sets will be used in this trial:

- Intention-to-Treat (ITT) Analysis Dataset this includes all randomized subjects
- Modified Intention-to-Treat Analysis Dataset (mITT) this includes all randomized subjects with at least one application of study drug
- Safety Analysis Dataset- this includes all randomized subjects with at least one application of study drug
- Per-Protocol Analysis Dataset this includes a subset of the subjects in the ITT analysis set who complied with the protocol sufficiently to ensure that these data would be likely to represent the effects of study intervention according to the underlying scientific model (e.g., subjects who took at least 80% of study intervention treatment for at least 80% of the initial 4 weeks).

A blinded data review will be conducted prior to unblinding of subject's treatment assignment. This review will assess the accuracy and completeness of the study database, subject evaluability, and appropriateness of the planned statistical methods. For descriptive statistics categorical data will be presented as frequencies and percentages. Percentages will be based on the number of subjects with non-missing values for the corresponding categorical variable. Continuous data will be presented as number of subjects with non-missing values, mean standard deviation, median, minimum and maximum, as well as the 25th and 75th percentile.

All statistical tests as well as the confidence intervals will be two-sided. The type I error probability for the confirmatory analysis is set to 5%. 95% confidence intervals are to be calculated, if feasible. Covariates for the primary analyses will be pre-specified. For secondary analyses these will be specified later in the SAP.

The primary efficacy and secondary analysis will be based on the mITT set. Most of primary and secondary variables such as T cell surface markers and plasma cytokine levels, and change and percent change from baseline to week 36 on markers of vascular inflammation and myocardial damages will be viewed as continuous variables and transformed as necessary. Each of efficacy variables will be analyzed using an Analysis of Covariance (ANCOVA) model with treatment as the fixed effect and other potential risk factors such as baseline value, clinical measures and demographic information as covariates. Differences between treatment groups and 95% confidence intervals will be estimated within the framework of ANCOVA. The statistical test for each of those variables will be a two-sided test at a significance level of 0.05 and no multiplicity adjustment will be done.

Timing of DSMB Meetings

Timeline	Type of Data
Prior to study dosing	Review charter, Review protocol, Select
, .	roles of DSMB members
Every Six Months	Enrollment summary, adverse events
	listings and tables for primary
	endpoints available.
Medical Monitor report	Review for determination of need for
every 12 weeks	additional DSMB review prior to next
	meeting
If two subjects have same	AE reviews, response to continue or
G4 event related to study	revert enrollment and dosing hold
drug	
If one or more subjects	Review of events with determination of
have mental status	study termination or continuance
changes, DIC, dyspnea,	
cytokine release syndrome	
or hypotension not	
remediated within 2-4	
hours and categorized as	
clinically relevant by PI and	
Medical Monitor with risk	
to participants	
Unanticipated Problem or	Review for determination of need for
non-SAE	additional DSMB review prior to next
	meeting
Upon completion or	Enrollment summary, adverse events
termination of study	listings and tables for primary
	endpoints available.

Study Termination

This study may be terminated under a variety of circumstances including, but not limited to, termination for overwhelming effectiveness, futility, or safety issues per protocol or DSMB monitoring guidelines. Responsibilities of the DSMB with regard to closeout will be to review the final study report to ensure study integrity. The DSMB may recommend continuing action items based upon the final review.

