A drug-related SAE of non-sustained ventricular tachycardia was experienced by 1 (16.7%) subject in the CD24Fc 60 mg group approximately 4 hours post-dose. The SAE was considered mild in severity by the Investigator and did not lead to discontinuation of the subject from the study. The Investigator considered the event to be drug related due to its close temporal proximity to dosing, though similar short, isolated episodes of non-sustained ventricular tachycardia may be seen in up to 4% of normal, healthy populations undergoing continuous cardiac monitoring. The other episode of non-sustained ventricular tachycardia was not considered related to study drug administration, and occurred without symptoms the second night post-infusion.

No deaths or adverse events leading to discontinuation occurred during the study. No clinically meaningful changes from baseline in laboratory parameters, vital signs, or ECGs occurred.

Exploratory Pharmacodynamic Markers:

As surrogate markers for treatment-emergent changes in basal levels of inflammation, pre- and postdose levels of interleukin-6 (IL-6) and high-sensitivity C-reactive protein (hs-CRP) were analyzed. Changes in fasting low-density lipoprotein cholesterol (LDL-C) levels were also analyzed. Interleukin-6 levels were determined from samples collected on Day -1; Day 1, 8 hours after dosing; Day 2; Day 7; and Day 42. The pre-dose levels of IL-6 were generally extremely low among the subjects, which did not allow for its use as a surrogate marker for CD24Fc anti-inflammatory activity in a normal, healthy population.

High-sensitivity C-reactive protein levels were determined from samples collected on Day -1, Day 7, and Day 42. Two additional time points (Day 1, 8 hours and Day 2) were added beginning with the last 6 subjects dosed in Cohort 2 (CD24Fc 30 mg group). The Day -1 hs-CRP levels were normal in all except 4 subjects. Overall, there were no significant treatment-emergent reductions in hs-CRP levels. Fasting LDL-C levels were determined from samples collected on Day -1, Day 7, and Day 42 for Cohort 1 (CD24Fc 10 mg group). Beginning with Cohort 2 (CD24Fc 30 mg group), this lipid sampling was expanded to include Day 14. At Day 14, the CD24Fc 240 mg group had a statistically significant percent change decrease in LDL-C from baseline.

 PK:

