In total, 1 (4.2%) patient died during the study due to TEAEs. Patient received placebo and experienced Grade 4 pneumomediastinum and Grade 5 pneumonia TEAEs that resulted in death. Per the Investigator, it was considered unlikely that these TEAEs were related to study drug.

In total, 9 (37.5%) patients experienced a treatment-emergent serious adverse event (SAE): 2 (33.3%) patients in the 240 mg CD24Fc single dose cohort, 1 (16.7%) patient in the 480 mg CD24Fc single dose cohort, 4 (66.7%) patients in the 960 mg CD24Fc multiple dose cohort, and 2 (33.3%) patients who received placebo. Treatment-emergent SAEs reported for patients who received CD24Fc were nausea, stomatitis, abdominal pain, dehydration, decreased appetite, device related infection, arthritis, polymyalgia rheumatica, weight decrease, cognitive disorder, and pulmonary embolism.

No patients experienced a study drug-related treatment-emergent SAE.

In total, the incidence of TEAEs of alanine aminotransferase increase and blood alkaline phosphatase increase were similar between patients who received CD24Fc and patients who received placebo. The incidence of TEAEs of aspartate aminotransferase increase was higher for patients who received CD24Fc compared to patients who received placebo. Treatment-emergent adverse events of blood cholesterol increase were only reported by patients in the 960 mg CD24Fc multiple dose cohort (2 [33.3%] patients). Treatment-emergent adverse events of blood creatinine increase were only reported by patients who received placebo do creatinine increase were only reported by patients who received placebo (2 [33.3%] patients). A TEAE of blood bilirubin increased was reported by 1 (16.7%) patient who received placebo.

In total, the incidence of TEAEs of white blood cell count decrease, lymphocyte count decrease, and neutrophil count decrease were higher in patients who received CD24Fc compared to patients who received placebo. The incidence of TEAEs of platelet count decrease was similar between patients who received CD24Fc and patients who received placebo.

No patient had a laboratory abnormality that was considered an SAE or resulted in discontinuation of study drug.

No patients who received either single or multiple dosing of CD24Fc had positive ADA results at any time point sampled pre- or post-infusion.

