7 STUDY INTERVENTION DISCONTINUATION AND PARTICIPANT DISCONTINUATION/WITHDRAWAL

7.1 DISCONTINUATION OF STUDY INTERVENTION

If a clinically significant finding is identified (including, but not limited to changes from baseline) after enrollment, the investigator or qualified designee will determine if any change in participant management is needed. Any new clinically relevant finding will be reported as an adverse event (AE).

AEs are evaluated according to the Division of AIDS (DAIDS) Table for Grading the Severity of Adult and Pediatric Adverse Events, version 2.1, July 2017. All adverse events will be reviewed by the Principal Investigator (PI) and the study team at team meetings. All Grade 3 events will be evaluated by the PI and the designated Medical Monitor. Grade 4 and Grade 5 events will be reported to the Sponsor and the Medical Monitor within 24 hours of notification of the event.

CD24Fc infusion will be paused for a single subject for any grade 4 event pending review by the Medical Monitor. The MM will include review of this event in a report issued to the DSMB every 12 weeks. Administration of medication will be paused for all subjects if 2 or more subjects have the same grade 4 adverse event deemed related to study drug. The MM will report these events to the DSMB and enrollment and dosing will be held for all pending review by the DSMB.

The study may be terminated after consultation with the Medical Monitor, DSMB and Sponsor, in the event that one or more of the following adverse reactions are not remediated within 2-4 hours, and in the opinion of the PI and Medical Monitor, are clinically relevant and constitute a substantial risk to the participants: cytokine release syndrome, hypotension, shortness of breath, disseminated intravascular coagulation, mental status changes.

Other criteria for study termination may include:

- the decision of the Medical Monitor or DSMB to stop further study visits
- the recommendation or decision for any reason of the PI that safety may be at risk or compromised by continuing the trial
- the decision of the Sponsor to terminate the study for any reason

The data to be collected at the time of study intervention discontinuation will include the following:

- Vital signs and physical examination
- Complete metabolic panel, complete blood count with differential, PT/INR
- Other laboratory tests that further evaluate a sign or symptom

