8.1.1.5 WEEK 2 VISIT

At this visit, a medication reconciliation will be done, as well as documentation and review of adverse events. The first 6 subjects who had PK samples done at Day 0 will also have PK blood samples obtained before and 2 hours after dosing of study drug. A window of +/- 10 minutes will be given around each post-infusion draw time point. ECG should be done prior to infusion and two hours post-infusion (+/- 10 minutes). The following laboratory tests will be done prior to drug dosing: CMP, CBC, urinalysis, HIV VL, CD4, PT/INR, lipid panel, urine hCG (for females of child-bearing potential), and research immunology and inflammation labs. A dose of CD24Fc, 240mg vs placebo, will be infused intravenously, pending no laboratory abnormalities or adverse events which warrant holding the study drug. He/she must be fasting prior to blood draw.

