8.4.9 PAUSING AND HALTING RULES

See Appendix A (Safety Monitoring Plan).

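### Outside five named reactions, a single drug-related death does not oblige a trial-wide pause or a 24-hour report to the DSMB

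*Combined protocol and SAP*

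**What the plan says.** The rules stand in two places. Section 7.1 says dosing is "paused for all subjects if 2 or more subjects have the same grade 4 adverse event deemed related to study drug", with enrollment and dosing then held for DSMB review. Appendix A, under Pausing and Halting Rules, repeats this as "If two subjects experience the same Grade 4 AE related to the study drug, all enrollment will be paused" and adds that the Medical Monitor reports to the DSMB within 24 hours.

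Appendix A has a second trigger: "If one or more subjects experiences changes in mental status, DIC, dyspnea, cytokine release syndrome and/or hypotension related to the study drug". It applies only where the reaction has not been remediated after 2-4 hours. This trigger also carries a 24-hour DSMB report, and enrollment and dosing are halted for everyone during the review. For the same reactions section 7.1 says only that the study may be terminated, so the mandatory halt comes from Appendix A.

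A single Grade 4 event pauses only the affected participant, and Appendix A states that the others are not paused. For the highest grades section 7.1 requires reporting: "Grade 4 and Grade 5 events will be reported to the Sponsor and the Medical Monitor within 24 hours". Section 8.4.9 adds no rule of its own.

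**The concern.** Safety and tolerability is the first primary objective. Pausing rules are written beforehand so that the response to a grave event does not rest on a decision made under pressure. Here the gravest grade is missing from them. After a related death outside the five reactions, whether other participants go on being dosed depends on someone choosing to act.

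The routine review schedule cannot be relied on to fill the gap. All three doses are given within 4 weeks, while the Medical Monitor reports to the DSMB every 12 weeks and the DSMB meets every six months. A participant could start and finish dosing between two scheduled reports.

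**Working it through.** The plan states no operating characteristic for its pausing rules, so there is no figure to reproduce. The check is mainly a comparison of texts.

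1. **Is Grade 5 covered by the word Grade 4?** Section 8.4.3.1 lists Grade 4 (potentially life-threatening) and Grade 5 (death) separately. Section 7.1 names both for 24-hour reporting, then only Grade 4 for pausing. Even if Grade 4 were read as Grade 4 or higher, the rule needs the same event in two participants, so one death would not meet it.

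2. **Do the five reactions cover it?** They do if the death followed unremediated, related mental status change, DIC, dyspnea, cytokine release syndrome or hypotension. Otherwise they do not.

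3. **Does the DSMB meeting table cover it?** It has event-driven rows for the two triggers and for unanticipated problems. The last leads only to a judgement on whether more DSMB review is needed before the next meeting. No row names a death.

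4. **Does SAE reporting cover it?** Section 8.4.7 and the SAE text in Appendix A foresee a causally related death and require immediate reporting, to the Medical Monitor and to the sponsor respectively. Neither ties it to a pause.

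5. **How do the rules rank events?** Section 8.4.5 records gradable laboratory abnormalities as AEs. So:

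| Event, judged drug-related, outside the five reactions | Mandatory trial-wide pause | DSMB told within 24 hours |
|---|---|---|
| Same Grade 4 laboratory abnormality in two participants | Yes | Yes |
| One death | No | Not required |

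6. **How often would an added one-event clause act?** In the earlier trials 48 people received CD24Fc: 5 × 6 = 30 in Phase I and 3 × 6 = 18 in Phase IIa. None had a drug-related death. Phase I had no deaths, and for Phase IIa the protocol states "No patients experienced a study drug-related treatment-emergent SAE". With 0 of 48, the one-sided 95% upper bound is 1 − 0.05^(1/48) = 6.1%. If a proportion p of the 32 planned CD24Fc participants had a related death outside the five reactions, the chance of at least one is 1 − (1 − p)^32: 27.5% at p = 1% and 47.6% at p = 2%. These rates are assumptions for illustration and are not forecasts.

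7. **How often would it act wrongly?** Relatedness is judged blind, so all 64 participants count. If a proportion q had a death wrongly judged related, the chance of an unnecessary pause is 1 − (1 − q)^64: 6.2% at q = 0.1% and 27.4% at q = 0.5%. Both rates are assumed. The documents give no death rate for this population.

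**The case against.** The strongest reply is that the gap is small and well watched. An acute related death would often pass through one of the five reactions, and one such participant already halts the trial. A delayed related death reaches the Sponsor and Medical Monitor within 24 hours. If it is unexpected, it goes to the FDA within 7 days and, as an unanticipated problem, to the IRB within 3. The Medical Monitor refers concerns to the DSMB and may stop the study (sections 8.3 and 8.4.7). Section 10.1.2 allows suspension for reasonable cause. Later doses are given "pending no laboratory abnormalities or adverse events which warrant holding the study drug". Appendix A allows termination for safety under the protocol or DSMB monitoring guidelines, and neither those guidelines nor the charter can be seen here. All of this stands, and it makes the gap narrow. It does not supply the obligation: each of these controls reports, reviews, acts on one participant, or permits a stop.

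A reader might infer more in two ways.

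First, that a death would go unexamined or that nobody could halt dosing. The controls just listed show otherwise.

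Second, that repeated related SAEs below Grade 4 also need a mandatory pause, since the programme's one drug-related SAE, non-sustained ventricular tachycardia, was rated low: "The SAE was considered mild in severity by the Investigator and did not lead to discontinuation of the subject from the study". The documents do not carry that far. The rating comes from an earlier trial whose scale is not stated, so it does not show how the event would grade under DAIDS 2.1. One can calculate that a two-participant SAE rule would fire with probability 14% to 99% among 32 people at true rates of 2.1% to 20%. But the 2.1% (1 of 48) is the rate of all related SAEs, not of one type, and the higher rates are assumed. False pauses also add up over event types. If 1% of 64 participants had a wrongly attributed SAE of a given type, the chance of two or more is 13%; over five independent types it is 1 − (1 − 0.135)^5, about 51%. Participants are aged 50 or over with raised cardiovascular risk, so blinded misattribution is plausible. Such a rule would also need event types matched in real time.

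**Conclusion.** The point holds in its narrow form. Outside the five reactions, the mandatory trial-wide pause is tied only to the same related Grade 4 event in two participants, and one related death triggers neither a pause nor a 24-hour DSMB report. What is missing is an obligation; the power to stop exists. The conclusion rests on section 7.1, section 8.4.9 and Appendix A as written, and the charter or DSMB guidelines could already close the gap. This is a matter of safety governance and changes no analysis.

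A pause for clusters of related SAEs below Grade 4 is a trade-off for the sponsor and DSMB to weigh. It is not a required correction, and the 14% to 99% figures should not be used to argue for it.

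**What to change.** Add to section 7.1 and to Appendix A: *One Grade 5 event judged potentially, probably or definitely related to study drug pauses all enrollment and dosing; the Medical Monitor reports it to the DSMB within 24 hours, and the pause holds until the DSMB decides.* The relatedness terms are those of section 8.4.3.2. Add a matching row to the DSMB meeting table in Appendix A, and keep the existing Grade 4 and five-reaction rules. If the charter already contains such a rule, repeat it here so that the documents agree.

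The change needs no new visit, sample or assessment. Its cost is an occasional short pause for a death wrongly judged related while blinded.
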